3.2.3 Stipend for Study Participation

Patients who participate in the study will receive a stipend for participation. Patients will be paid up to \$200 in the form of prepaid debit cards worth \$50 after each study visit (Baseline, 1-month, 3-month, and 6-month).

3.3 Study Observations, Procedures and Evaluation Criteria

The study is a decentralized trial. All study visits required for the completion of the trial will occur in the home or will be done virtually. Eligible subjects will be pediatric and adult patients ages 5 – 80 who are able to perform OLE therapy using a mouthpiece, mask, or trach adaptor and who meet all inclusion and none of the exclusion criteria. Informed consent (and assent if minor subject) will be obtained prior to enrollment in the study. Demographic and medical history data will be collected from the medical record of each subject at the time of enrollment.

3.3.1 Informed Consent:

Informed consent (and assent if minor subject) will be obtained from the patient or legally authorized representative prior to enrollment in the study. Informed consent will be obtained by the principal investigator or his/her representative.

3.3.2 Selection Criteria:

Inclusion and exclusion criteria will be reviewed and documented for all study subjects (criteria are described in section 3.2 above).

3.3.3 Study Visits and Data Collection Procedures:

All study subjects will complete a virtual home baseline study visit for initiation of the trial and enrollment into the study. Following the baseline visit, each study subject will complete three follow-up visits. The first follow-up visit will be approximately one month after initiating therapy

PROTOCOL TITLE

Evaluation of Oscillation and Lung Expansion (OLE) using The Volara® System for treatment of respiratory complications in patients with neuromuscular disease in the home setting

Final Protocol

Protocol Number: CR-RR-2020-005**Date:** 11May2022

and will occur virtually or by phone. Follow-up visits two and three will be done virtually and will occur approximately three months and six months after initiation of OLE therapy. Pulmonary function measures will be collected at baseline and at the end of each month of therapy during the active treatment period. Study Visits and procedures for data collection is described below.

3.3.3.1 Baseline Study Visit: During the baseline visit, study staff will review the informed consent form (and assent form if minor subject) with the study subject and/or caregiver(s). If the patient/caregiver agrees to participate in the study, the informed consent form (and assent form, if applicable) will be signed. A pregnancy test will be administered to female subjects of childbearing age. Inclusion and exclusion criteria will then be assessed and documented and (if eligible) the subject will be enrolled in the study. The study schedule and subject responsibilities will then be reviewed with the subject/caregiver. During the Baseline Visit, the subject's current respiratory therapy regimen and required respiratory support will be documented. A quality of life (QOL) assessment using the Severe Respiratory Insufficiency (SRI) questionnaire will be completed for each subject to assess QOL rating during the pre-treatment period and a Satisfaction Survey questionnaire will be completed by the subject and/or caregiver as an assessment of the current therapy regimen.

3.3.3.2 Documentation of Demographics, Medical History and Pulmonary Exacerbations: Demographic data will be collected for patients enrolled in the study. Medical records for each enrolled subject will be obtained and reviewed to obtain relevant patient medical history and to document pulmonary comorbidities and history at the time of enrollment. Current respiratory related medications and treatments will be documented. Pulmonary exacerbations (as defined in the study endpoints) that occurred in the 12-month period prior to enrollment in the study will be documented. Subsequent medical records will be obtained during the active treatment period and will be used to determine and to document the occurrence of pulmonary exacerbations during that period.

- **Demographic Data**

The following demographic data will be collected: Age, Height, Weight, Race, Ethnicity and Gender.

PROTOCOL TITLE

Evaluation of Oscillation and Lung Expansion (OLE) using The Volara® System for treatment of respiratory complications in patients with neuromuscular disease in the home setting

Final Protocol

Protocol Number: CR-RR-2020-005

Date: 11May2022

- **Pulmonary Related Medical History**

History of asthma, cystic fibrosis, bronchiectasis, COPD, obstructive sleep apnea, documented obesity (BMI $\geq 30 \text{ kg m}^2$), other pulmonary condition(s) will be documented.

- **Medications**

Respiratory related medications such as bronchodilators, or mucolytics that are prescribed for each study subject during the 12-month pre-treatment period, as well as respiratory medications that are prescribed during the active treatment period will be documented.

- **Respiratory Status**

Respiratory status including required respiratory support (e.g., invasive mechanical ventilation, noninvasive ventilation, requirement for tracheostomy, O₂ level, etc.) will be documented from the patient medical record for each subject.

- **Respiratory Treatments**

Respiratory treatments, including mechanical insufflation/exsufflation or other lung expansion or airway clearance therapy, or other therapies to improve respiratory status will be documented from the patient medical record.

- **Pulmonary Exacerbations**

Pulmonary exacerbations (as defined in the study endpoints) which occurred during the 12-month pre-treatment period or during the active treatment period will be documented.

3.3.3.3 Pulmonary Function Testing: Pulmonary function testing will be completed virtually by an external research organization which specializes in home pulmonary function testing (Zephyrx). This testing will be scheduled separately following enrollment into the study. Baseline parameters will be assessed, including slow vital capacity (SVC), Peak Cough Flow (PCF), Resting SpO₂, and Maximal Inspiratory Pressure (MIP). With this study population, certain subjects may not be able to complete a valid test for all pulmonary function procedures. If unable to complete, a procedure, the inability to complete that procedure will be documented.

PROTOCOL TITLE

Evaluation of Oscillation and Lung Expansion (OLE) using The Volara® System for treatment of respiratory complications in patients with neuromuscular disease in the home setting

Final Protocol

Protocol Number: CR-RR-2020-005

Date: 11May2022

3.3.3.4 Run-in Period: Following the Baseline Study Visit, a run-in period of two to four weeks will be completed by the subject prior to initiation of OLE therapy. During this period, the subject/caregiver will document use of MIE and other current airway clearance and lung expansion therapy/maneuvers for each day in the run-in period.

3.3.3.5 Home Training on The Volara® System: A Hillrom designated trainer will set up the device and review operation and treatment protocol at the time the device is delivered. Study subjects and caregivers will be instructed to use the device as their primary airway clearance and lung expansion therapy for a period of six months. Hillrom training staff will follow up with each Volara user according to the standard device placement and follow-up program.

3.3.3.6 Adherence Documentation: During the six-month follow-up period, adherence to the daily prescribed therapy regimen will be assessed. The Volara® System logs therapy details for each therapy completed, including the total time of therapy, the number of stages completed, the total time in CPEP mode, total time in CHFO mode and peak pressures achieved in each mode. Adherence data logs will be downloaded on a regular basis during the active treatment period.

3.3.3.8 One-month Virtual Study Visit: A one-month study visit with each study subject will be conducted virtually. Visits will be completed +/- 3 days from the one-month scheduled visit date. During this visit, the following procedures and assessments will be conducted:

- Review of study procedures with subject/caregiver
- Review of current respiratory status, respiratory treatments, and medications
- Documentation of patient/caregiver reported exacerbations and medical interventions for the prior period (run-in and first month of Volara therapy)
- Documentation of any Adverse Device Effects that the subject experienced during the follow-up period
- Completion of QOL questionnaire
- Completion of Patient/Caregiver Satisfaction survey

3.3.3.9 Three-month and Six-month Virtual Study Visits: Three-month and six-month study visits with each study subject will be conducted virtually by study staff. Visits will be completed

PROTOCOL TITLE

Evaluation of Oscillation and Lung Expansion (OLE) using The Volara® System for treatment of respiratory complications in patients with neuromuscular disease in the home setting

Final Protocol

Protocol Number: CR-RR-2020-005**Date:** 11May2022

+/- 3 days from the one-month scheduled visit date. During these visits, the following procedures and assessments will be conducted:

- Review of study procedures with subject/caregiver
- Review of current respiratory status, respiratory treatments, and medications
- Documentation of patient/caregiver reported exacerbations and medical interventions for the prior period (three-months of Volara therapy)
- Completion of QOL questionnaire
- Completion of Patient/Caregiver Satisfaction survey

3.3.3.10 Monthly Pulmonary Function Measure Visit: Monthly virtual visits with each study subject will be conducted virtually in the subject's home by the pulmonary function specialists. Visits will be completed +/- 3 days from the one-month scheduled visit date. During these visits, the following procedures and assessments will be conducted:

- Slow Vital Capacity (SVC)
- Peak Cough Flow (PCF)
- Resting O2 Saturation (SpO2)
- Maximal Inspiratory Pressure (MIP)

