| | 
• Airway Clearance Satisfaction surveys will be conducted. Results from the active treatment period will be compared to the baseline period, during which the subject received his/her regular airway clearance regimen.Any device related adverse events which occur after initial therapy with The Volara® System will be recorded.Any equipment related complaints which occur after initial therapy with The Volara® System will be recorded. |
| Subject Withdrawal: | Subjects may withdraw consent to participate in the study at any time. The subject may also be withdrawn from the study according to investigator judgement regarding the continued health or safety of the subject or related to inability or unwillingness to perform study therapy or procedures. Removal of subjects may occur for any of the following reasons: 
• Subject enrolled in violation of inclusion/exclusion criteria• Inability to tolerate OLE therapy• Adverse event or adverse device effect that occurs during therapy• Physician judgement that the patient is not a good candidate for the study• Inability or unwillingness to perform OLE therapy and data collection maneuvers as directed |
| Statistical Methods: | Descriptive summary statistics will be provided for demographics, the primary and secondary endpoints. Continuous data will be summarized with N, mean, median, standard deviation, min, and max. Categorical data will be summarized with the number and percent of patients in each category. Incidence of adverse device effects (ADEs) will be tabulated. |

PROTOCOL TITLE

Evaluation of Oscillation and Lung Expansion (OLE) using The Volara® System for treatment of respiratory complications in patients with neuromuscular disease in the home setting

Final Protocol

Protocol Number: CR-RR-2020-005

Date: 11May2022

| | |
|--|---|
| | Incidence of device-related complaints will be tabulated. |
|--|---|

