3.3.5 Study Observations/Procedures Table

The study observations and documentation timeline are outlined in Table 1.

PROTOCOL TITLE

Evaluation of Oscillation and Lung Expansion (OLE) using The Volara® System for treatment of respiratory complications in patients with neuromuscular disease in the home setting

Final Protocol

Protocol Number: CR-RR-2020-005

Date: 11May2022

TABLE 1

Study Observations/Procedures

| Procedures | Baseline | Run-in | 1 month | 3 months | 6 months |
|---|------------------------------------|--------|---------|----------|------------------------------|
| Inclusion/Exclusion Criteria | X | | | | |
| Pregnancy test (women of childbearing age) | X | | | | |
| Informed consent (and assent if minor subject) | X ¹ | | | | |
| Demographics | X | | | | |
| Medical History | X | | | | |
| Baseline Pulmonary Medications | X | | | | |
| Documentation of acute pulmonary exacerbations: 
 Hospital admission and discharge (including ICU admission and discharge) Antibiotic use (IV/Oral/inhaled) start and stop dates Outpatient Visits for Pulmonary Complication 
 Physician Office Visits Urgent Care Visits ED Visits Documented from the medical record | X Retrospective (past 12 mo) | | | | X Active Treatment Period |
| QOL Questionnaire | X | | X | X | X |
| Patient/Caregiver satisfaction with Therapy | X | | X | X | X |
| Basic Pulmonary Function Measures 
 SVC PCF Resting SpO₂ Maximal Inspiratory Pressure (MIP) | X | | | | Monthly |
| Adherence to prescribed regimen (OLE) | | | | | Ongoing |
| Documentation of use of MIE or other airway clearance/lung expansion therapy/maneuvers | | X | | | |
| Adverse device effects | | | | | Each Occurrence |
| Study Exit Form | | | | | X |

PROTOCOL TITLE

Evaluation of Oscillation and Lung Expansion (OLE) using The Volara® System for treatment of respiratory complications in patients with neuromuscular disease in the home setting

Final Protocol

Protocol Number: CR-RR-2020-005

[figure not shown]
Date: 11 May 2022

¹Obtained prior to any study-specific procedures

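### The protocol schedules an adverse device effect question only at the 1-month visit, so about five of the six months of home use have none

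*Protocol*

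**What the plan says.** Subjects are told to "use the device as their primary airway clearance and lung expansion therapy for a period of six months" (protocol 3.3.3.5). All study visits are virtual or in the home.

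- **1-month visit (3.3.3.8).** One of its six items is "Documentation of any Adverse Device Effects that the subject experienced during the follow-up period". The exacerbation item in the same list is worded "for the prior period (run-in and first month of Volara therapy".
- **3- and 6-month visits (3.3.3.9).** One shared list of five items. The event item is "Documentation of patient/caregiver reported exacerbations and medical interventions for the prior period (three-months of Volara therapy". No item mentions device effects.
- **Monthly lung-function contacts (3.3.3.10).** "Monthly virtual visits with each study subject will be conducted virtually in the subject's home by the pulmonary function specialists". The content is SVC, PCF, SpO2 and MIP. Section 3.3.3.3 assigns this testing to an external organization.
- **Synopsis, Methods.** Any "device related adverse events which occur after initial therapy with The Volara® System will be recorded".
- **Table 1 (3.3.5).** The ADE row reads "Each Occurrence", with no mark at the 1-, 3- or 6-month visit.
- **Section 5.0.** Safety surveillance and reporting by the investigator last until the final study test, the end of participation or withdrawal. Reports are due to the sponsor within 24 hours of awareness. The section does not say how subjects are to be asked.
- **SAP 2.5.1.2 and Appendix 1.** Treatment-emergent and device-related events are summarized over the whole treatment period, by system organ class, preferred term, severity and relationship to the device.

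**The concern.** A duty to record an event is not a way of hearing about it. In a home-based study the investigator sees little directly, and the 24-hour clock in section 5.0 starts only at awareness. The protocol recognizes this at month 1 by writing a specific ADE item into the visit. It then drops the item from the two visits that cover the rest of the exposure and gives no reason.

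Section 1.2 says there have been no formal clinical studies of this device, section 5.1.1 allows for unforeseen risks, and the Synopsis names ADE incidence as a planned tabulation. If subjects are asked directly about device effects for one month and not for the next five, the pooled incidence mixes two levels of ascertainment. Effects that need no medical care and do not end participation are the ones most easily lost.

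**Working it through.** The documents state no figure on this point. The sample of about 70 is a convenience sample with no power calculation, so there is nothing to reproduce first.

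**1. The visit lists side by side**

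| Item | 1 month (3.3.3.8) | 3 and 6 months (3.3.3.9) | Monthly lung function (3.3.3.10) |
|---|---|---|---|
| Review of study procedures | yes | yes | no |
| Respiratory status, treatments, medications | yes | yes | no |
| Reported exacerbations and interventions | yes | yes | no |
| Adverse device effects | **yes** | **no** | **no** |
| Quality-of-life questionnaire | yes | yes | no |
| Satisfaction survey | yes | yes | no |
| SVC, PCF, SpO2, MIP | no | no | yes |

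The ADE item is the only item that separates the first list from the second. Section 3.3.3.9 even keeps the window sentence of the 1-month visit, "Visits will be completed +/- 3 days from the one-month scheduled visit date", which suggests that one list was edited from the other and that the omission is a drafting slip.

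**2. Share of exposure after the only listed ADE item**

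Inputs: 6 months of therapy (3.3.3.5); ADE item at month 1 (3.3.3.8); window of 3 days either side (3.3.3.8 and 3.3.3.9). I assume that the window in 3.3.3.9 applies to the 6-month date. One month = 365.25 / 12 = 30.4 days, and six months = 182.6 days.

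Formula: share = (total exposure - time to the 1-month visit) / total exposure.

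- On schedule: (182.6 - 30.4) / 182.6 = 152.2 / 182.6 = 83.3%, which is 5/6.
- Smallest (1-month visit 3 days late, 6-month visit 3 days early): (179.6 - 33.4) / 179.6 = 146.2 / 179.6 = 81.4%.
- Largest (1-month visit 3 days early, 6-month visit 3 days late): (185.6 - 27.4) / 185.6 = 158.2 / 185.6 = 85.2%.

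With 70 subjects and full follow-up, this is up to 70 x 5 = 350 of 70 x 6 = 420 person-months.

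**3. What the other routes after month 1 can reach**

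- The status review and the exacerbation and intervention item are likely to pick up events that changed respiratory status or needed care.
- Medical records in the treatment period are reviewed for pulmonary exacerbations (3.3.3.2), not for ADEs.
- The satisfaction and quality-of-life questionnaires may prompt a remark, but neither is described as a source of ADEs.
- Device complaints are reportable (5.0), but someone has to raise one.
- The exit form catches an effect only if it ends participation.

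A subject who has headaches or hyperventilates with the device (both listed in 5.1.1), carries on with therapy and seeks no care may pass through all five without being recorded.

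**4. After the change**

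With the item at 1, 3 and 6 months, the questions cover months 0-1, 1-3 and 3-6: 1 + 2 + 3 = 6 of 6 months.

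**The case against.** The best reply is that safety collection does not stop at month 1. Section 5.0 gives the investigator a continuing surveillance duty to the end of participation. The Synopsis and Table 1 require every ADE to be recorded. There are structured contacts at 3 and 6 months, complaints go to the sponsor within 24 hours, and the SAP's discontinuation reasons include an adverse device effect. The case report form, the satisfaction items and the sponsor's device follow-up program are not among the documents and may contain a prompt. The SAP's adverse event analyses also imply data collection wider than the protocol's visit lists.

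Most of this stands, and it rules out two stronger readings. A reader might infer that ADEs after month 1 rest wholly on spontaneous reports, or are not collected. The documents do not support that, because surveillance continues and several indirect routes exist. A reader might also infer that the safety tables will look better after month 1. No planned safety table splits events by month; only the listings carry start dates.

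It can also be said that this is a descriptive pilot of a cleared device and that ADEs are not a named endpoint. That limits the severity. It does not remove the gap, because ADE incidence is still a planned result and nothing in the documents names a later scheduled question.

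**Conclusion.** The point holds as a gap in scheduled elicitation. The only listed ADE item is at month 1, and about 5 of 6 months of home exposure (81-85%) follow it. In that time awareness depends on unprompted reports or on partial, indirect capture. The pooled device-related incidence would tend to be understated, mainly for mild effects.

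The size of that understatement cannot be derived. The documents give no ADE rate and no capture probability, so any percentage would only restate assumed values. The direction rests on two assumptions: that a direct question finds more mild events than no question, and that the unseen forms and device follow-up do not already ask it. The SAP inherits the unevenness, since it pools events over the treatment period without comment. The primary endpoint is not affected. The change should be made, but the study does not fail without it.

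**What to change.** Add the ADE item of 3.3.3.8 to the list in 3.3.3.9 for both visits, with the recall period stated as the time since the previous study visit so that an event is not counted twice. In Table 1, mark ADE collection at 1, 3 and 6 months and keep "Each Occurrence". If a form or the device follow-up program already asks the question, cite it in section 5.0.

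SAP version 2.0 (28 May 2024) describes study conduct in the past tense in 2.6.2, so follow-up may be over. In that case, state in the SAP and the report that scheduled ADE elicitation was specified only at month 1 and that later events came from continuing surveillance and indirect routes.

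The cost is one bullet and one table row, with no new visit or procedure. Expect a few more minutes per visit and probably a higher reported ADE count. Recall would still span up to three months at the last visit, so some mild events could be missed even then.

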### 2.1.3 Visit Windows

The study visits for the active treatment period can be obtained from the eCRF and need not be derived programmatically. The visits will be displayed as: Baseline, 1-month, 2-month, 3-month, 4-month, 5-month, 6-month.

Results from unscheduled study visits will not be included in table summaries. These values will only be presented in the listings.

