#### **2.4.2.1.2 Analysis of Pulmonary Function Tests**

Pulmonary function tests (SVC, PCF, SPO2, MIP) that were acceptable by ATS Standards, deemed the 'Best Measurements' for the series based on ATS acceptability, and completed in accordance with the study protocol will be analyzed descriptively at each time-point (Baseline, 1-month, 2-month, 3-month, 4-month, 5-month, 6-month), using n, mean, standard deviation, minimum, median, and maximum. Change from baseline values will also be presented in a similar manner. Subjects with SPO2 measures collected in the same setting across all study visits will be tabulated. SPO2 measures across all settings will be listed.

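### The windows for later visits are tied to the one-month date, and the SAP does not say whether its protocol-compliance condition on lung-function tests includes timing

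*Protocol*

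**What the plan says.** **Intended timing.** Protocol 3.3.3 states that follow-up visits two and three "will occur approximately three months and six months after initiation of OLE therapy". For lung function it states: "Pulmonary function measures will be collected at baseline and at the end of each month of therapy during the active treatment period".

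**Windows.** Three consecutive visit descriptions use one sentence:

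- 3.3.3.8, one-month visit: "Visits will be completed +/- 3 days from the one-month scheduled visit date. During this visit, the following procedures and assessments will be conducted". Here the anchor is right.
- 3.3.3.9, three- and six-month visits: plus or minus "3 days from the one-month scheduled visit date. During these visits, the following procedures and assessments will be conducted".
- 3.3.3.10, monthly lung-function visits: "Visits will be completed +/- 3 days from the one-month scheduled visit date".

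**Analysis.** SAP 2.4.2.1.2 sets three conditions for a lung-function test to be tabulated. It must be acceptable by ATS standards, it must be the best measurement of its series, and it must be "completed in accordance with the study protocol will be analyzed descriptively at each time-point (Baseline, 1-month, 2-month, 3-month, 4-month, 5-month, 6-month". The phrase about the protocol is not defined.

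SAP 2.1.3 is titled as a section on visit windows but gives no range of days. It says instead: "The study visits for the active treatment period can be obtained from the eCRF and need not be derived programmatically". It keeps results from unscheduled visits out of the tables and shows them only in listings.

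**The concern.** A window centred on month 1 cannot contain a visit at month 3 or month 6. On a literal reading it cannot contain a lung-function test at months 2 to 6 either. On its own this would be a slip in the visit schedule. It matters more here because SAP 2.4.2.1.2 makes agreement with the protocol a condition for entering the lung-function tables, and the protocol's timing rule is faulty for most of the tests that the condition governs.

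Two things are at stake. First, it is left open which lung-function results count. A valid test done a few days late could be kept by one programmer and dropped by another, and in an open-label, pre-post study that choice should not be made after the data are seen. Second, SAP 1.3.2 tabulates protocol deviations for the full analysis set. If every three- and six-month visit is a deviation by definition, that table says little about conduct.

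**Working it through.** The plan gives no figure to reproduce: the sample is a convenience sample and there is no formal test. The check is date arithmetic, followed by a comparison of the two documents.

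**Step 1. Literal window.** Let a month have *m* days, so that month *k* falls on day *k·m* from the start of therapy. The literal window is *m* − 3 to *m* + 3. For *k* ≥ 2, the distance past its upper edge is

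*k·m* − (*m* + 3) = (*k* − 1)·*m* − 3.

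The documents do not define the length of a month, so I assumed 28, 30 and 30.44 days in turn. The windows are days 25–31, 27–33 and 27.4–33.4.

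| Month *k* | Day, if *m* = 30 | Inside window? | Days past upper edge, *m* = 28 / 30 / 30.44 |
|---|---|---|---|
| 1 | 30 | yes | – |
| 2 | 60 | no | 25 / 27 / 27.4 |
| 3 | 90 | no | 53 / 57 / 57.9 |
| 4 | 120 | no | 81 / 87 / 88.3 |
| 5 | 150 | no | 109 / 117 / 118.8 |
| 6 | 180 | no | 137 / 147 / 149.2 |

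Read literally, 5 of the 6 monthly tests and both later study visits are out of window for every month length tried. The smallest miss is 25 days.

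**Step 2. Is another reading available?** Section 3.3.3.10 stands under a heading for monthly visits, so its anchor could mean the due date of each one-month interval. Section 3.3.3.9 concerns only months 3 and 6, and that reading does not fit there.

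**Step 3. What could the SAP condition mean?** The two conditions before it already deal with test quality, so the third should add something. It could refer to how the test was conducted. It could also refer to timing, because the ±3 days is the only numerical requirement in 3.3.3.10. Nothing in the SAP settles this.

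**Step 4. Which results depend on it?** Only the lung-function tables. The SAP sections on quality of life (2.4.2.8.2) and satisfaction (2.4.2.9.2) carry no such condition. The primary endpoint counts exacerbations from records by study period and uses no visit window.

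**Step 5. Windows anchored to each visit's own date.** With *m* = 30 they are days 27–33, 57–63, 87–93, 117–123, 147–153 and 177–183. They do not overlap, and all six tests can qualify.

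**The case against.** The strongest reply is that the SAP shows what is meant. The sentence that contains the condition also names every month from 1 to 6 as a time-point to be analysed. SAP 2.1.3 takes the visit from the eCRF without a date check, so a late scheduled test keeps its nominal month. The 3.3.3.9 wording looks like text carried over from 3.3.3.8. This reply stands as far as intent goes, and it rules out some stronger conclusions that a reader might draw:

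- **That all tests after month 1 will be excluded.** A reading that empties five time-points named in the same sentence is not a fair one.
- **That a test done four days late is certainly discarded.** This requires the compliance phrase to include timing, and the SAP does not say so.
- **That the filter flatters the on-treatment course.** It is plausible that subjects who are ill or in hospital are tested late, but the documents do not show it. The effect would also depend on the previous point.
- **That the loss can be sized.** If 10% to 20% of tests were out of window (assumed rates), 70 × 0.10 = 7 to 70 × 0.20 = 14 subjects would be lost per time-point, and 1 − 0.9⁶ = 47% to 1 − 0.8⁶ = 74% would lose at least one of six tests. The rates have no source in the documents. Independence fits poorly with lateness that clusters in ill subjects, and Protocol 3.3.3.3 expects that some subjects cannot give every valid test. For SVC, PCF and MIP the SAP summarises each time-point separately, so losing one test does not remove a subject from the others.

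The effect on deviations is also limited. SAP 1.3.1 removes subjects from the per-protocol set only for deviations that could affect the primary endpoint.

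The reply does not repair 3.3.3.9, does not define the compliance phrase, and does not say what happens to a test outside ±3 days. A late test recorded as unscheduled would leave the tables by a separate route, under SAP 2.1.3.

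**Conclusion.** The point holds as an inconsistency in an operative rule that can reach a secondary endpoint. The window in 3.3.3.9 is wrong as written. The one in 3.3.3.10 is wrong or at best ambiguous. The SAP condition that may rely on them is undefined. Taken literally, 2 of the 3 follow-up visits are deviations, and so are 5 of the 6 monthly lung-function tests unless 3.3.3.10 means each monthly due date. These counts hold for month lengths of 28 to 30.44 days.

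The practical risk is that valid tests after month 1, or tests a few days off schedule, are dropped or kept by a decision that the plan does not fix in advance. How many tests this would affect, and in which direction it would move the summaries, cannot be determined from the documents. Lung function is secondary and descriptive, so this should be corrected but does not threaten the main result.

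**What to change.** 1. **Protocol 3.3.3.9 and 3.3.3.10.** Anchor the ±3 days to the scheduled date of the visit concerned, counted from the Volara start date.
2. **SAP 2.4.2.1.2.** State that accordance with the protocol refers to how the test was conducted. Keep every ATS-acceptable scheduled test (the best of its series, as now) under its eCRF visit label, whether or not it met ±3 days. Flag out-of-window tests in Listing 16.2.6.2.

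Keeping the eCRF label is better than reassigning tests to the nearest monthly target day. With 30-day months, a month-2 test done on day 76 would move to month 3 (14 days from day 90, 16 from day 60) and could collide with the real month-3 test.

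**Cost.** No new data are needed. Test dates within a nominal month will spread slightly more. The protocol correction needs the agreement of sponsor, investigators and IRB/EC that Protocol 8.0 requires. SAP 2.6.2 already describes the study in the past tense. If visits are complete, the SAP change alone is enough, provided that it is made before the tables are produced.
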